**The following procedures are in place:**

- We do not collect any subject identifiers that we do not need.
- We remove/destroy subject identifiers as soon as they are no longer needed.
- We restrict physical access to any area or computer system that contains subject identifiers.
- Restrict *electronic* access to any computer system that contains subject identifiers.
- Subject identifiers are stored electronically via REDCap and will not be exported with research data that is analyzed. All information collected in this study is confidential and all data will be transformed into anonymously coded identifiers for each subject prior to analysis.
- Subject identifiers and contact information are never distributed outside of University of Illinois at Chicago.

## **12.0 STATISTICAL CONSIDERATIONS**

### ***Outcomes, Analysis Methods and Sample Size***

**Statistical Analysis Plan:** Outcome analyses will be conducted within the UIC Institute for Minority Health virtual environment. Descriptive statistics will be used to assess completeness of study data, normality of outcome measures, and potential covariates as well as to identify potential covariate imbalances between study arms. Based on our pilot study work and our protocol, which emphasizes repeated telephone contacts with participants' post-baseline, we anticipate relatively low loss to follow up at 3 and 6 (at most 20%). For the primary analysis of each study hypothesis we will initially adopt an "intention to treat", (ITT) modality. We will apply the independent samples t-test and Chi-squared test to compare key measures between

treatment arms to ascertain balancing of important measures that may have an influence on the outcome variables. All statistical analysis will be conducted using SAS 9.4 (SAS Institute Inc., Cary, NC, USA) and R version 3.3.1. A brief description of the analytical plan by specific aim follows:

Aim 1: Evaluate the effectiveness of an ED-based E intervention with PACHT-c intervention (arm 2) on the primary outcome of *mean SBP difference* at 6 -months post-intervention compared to usual care (arm 1).

Aim 2: Evaluate the effectiveness of an ED-based E intervention with PACHT-c on the secondary outcome of *mean SBP and DBP differences* at 3-months and 12-months and *mean DBP differences* at 6 months post-intervention compared to usual care.

Aim 3: Examine if the E intervention reduces racial disparities. Specifically, if the intervention is as effective in racial minorities as non-minorities. This will be an exploratory analysis and will primarily focus on changes in cardiovascular risk score/profile. Also included will be an assessment of intervention mediators: primary care engagement, medication adherence, and HTN knowledge in these same patients at 3 and 6 months post randomization-intervention

*Aim 1:* We hypothesize that the mean change in SBP at 6 months after randomization will be higher in the intervention arm compared to usual care. Linear regression models will be used to compare change in continuous BP between treatment arms at 6 months; mixed effects linear regression models will be used to combine the two-time points into a single model.

*Aim 2:* We hypothesize that the mean change in SBP and DBP at 3 and 12 months and mean DBP at 6 months after randomization will be higher in the intervention arm compared to usual care. Linear regression models will be used to compare change in continuous BP between treatment arms at 3 months and DBP at 6 months; mixed effects linear regression models will be used to combine the two-time points into a single model.

*Aim 3:* Change in the cardiovascular risk score at 3 and 6 months will be analyzed to assess racial disparity by testing the interaction between a binary indicator of treatment group and a binary indicator of minority versus non-minority. The distribution of change scores will be examined to determine whether linear regression is appropriate; if not, ordinal categories will be defined and proportional odds logistic regression will be used. Models will be fit at each of 3

and 6 months, and mixed-effects models will be used to combine the two-time points into a single model.

*Handling Missing Data:* For the missing data analysis an ITT will be implemented. Furthermore, missing data will be handled by using a mixed-effects model approach, which assumes that the data is missing at random and hence will not bias the analysis. If we determine that data may not be randomly missing and thus non-ignorable then two well accepted approaches to handle this situation will be implemented, namely selection models and pattern mixture models.

*Other Statistical Considerations:* Sampling balance for the key predictors will be checked and adjusted for in the analysis, and their mediating and moderating effects will be examined if needed. We address power for Aims 1 and 2 for unadjusted tests. Adjustment for covariates will decrease power slightly by using up degrees of freedom, but the adjustment will also create more accurate estimates, so the expected power will be similar.

Effect Size		80% Power		85% Power	
Standardized	mmHg*	Sample Size		Sample Size	
	DBP	SBP	N	N**	N
0.20	2.40	4.20	786	1049	898
0.25	3.00	5.25	504	673	576
0.30	3.60	6.30	350	467	400
0.35	4.20	7.35	258	345	294
0.40	4.80	8.40	198	265	178
0.45	5.40	9.45	156	209	178
0.50	6.00	10.5	126	169	144
*Effect size is defined as difference in means divided by standard deviation. From our pilot study: DBP Standard deviation 12 mmHg; SBP Standard Deviation 21 mmHg.					
**25% attrition is assumed and thus required sample size, N**, is obtained by dividing calculated sample size, N, by 0.75.					

*Sample Size:* The primary hypothesis of the study is that the difference in systolic blood pressure from baseline to month 6 is different across the two treatment arms. Testing this hypothesis amounts to testing difference in mean systolic blood pressure between the two treatment groups at 6 months, due to randomization (since the mean SBP at baseline is the same across groups). Thus, sample size estimation is determined by comparing

the mean SBP at 6 months using a two-sample, two-sided, 5% significance t-test with 80% and

85% statistical power. Sample size is calculated first to detect a pre-determined effect size (difference in means divided by standard deviation) and then converted to blood pressure units, namely mmHg. Data from our pilot study resulted in estimates of DBP standard deviation of 12 mmHg and SBP standard deviation of 21 mmHg. For example, the required sample size to detect an effect size of 0.25 ( $0.25*12 = 3$  mmHg in DBP, and  $0.25*21 = 5.25$  mmHg in SBP) is 504 for 80% power and 576 for 85% power, using a two-sided, two-sample 5% significance t-test. An attrition-adjustment to the calculated sample size give 673 and 770 patients for 80% and 85%, respectively.

*The statistical analysis:* Mean BPs will be compared across groups using a two-sample, two-sided, 5% significance t-test. The analysis will be then extended to gain statistical power by adjusting the comparison by baseline BP levels. An intention-to-treat analysis will be undertaken by using mixed effects models so that all the available information on each patient is used for the analyses. Further analyses using maximum likelihood estimators for data imputation and weighting will be implemented to better account for missing data. Moreover, key variables (age, sex, race/ethnicity) will be compared across treatment groups and if different will be used in a multivariate mixed effects model.

*Patient Accrual:* Using the UI Health Enterprise Data Warehouse (EDW), a report was developed to estimate how many patients seen in the ED had elevated BP (Stage 1  $\geq 140/90$  mmHg). The sampling was conducted from April 1, 2014 to December 31, 2014 (9 months). During the sampling period, 8,021 patients had BP readings of at least 140/90 mmHg (29.16 patients per day) as the final ED BP measurement. Approximately 69% of these patients were discharged. The proposed study requires enrollment of 13.9% (770/5534) of potentially eligible UI Health patients over a 4-year period. We are confident that we can meet our recruitment goals.

**Data Management:** Electronic data entry will utilize REDCap (Research Electronic Data Capture). REDCap is a secure, web-based application providing data quality control through validation options, audit trails and user access controls. Study information within the virtual environment will be available for participant tracking activities. Data quality related to the entry

process can be controlled by programming REDCap validation options. Tracking reports will be reviewed with study staff every two weeks. Statistical analyses prior to the 3, 6, and 12-month outcome evaluations will be limited to quality control, enrollment and dropout reporting, and participant demographics. No interim looks are anticipated, but quality control and data entry errors and omissions will be continuously monitored and reported to staff for remediation. Many of the needed REDCap forms for the TOUCHED proposal were already developed for use for the R56 pilot study.

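### Age, sex and race/ethnicity enter the mixed-effects BP model only if the arms differ on them, so chance imbalance picks the covariates and most of their precision is usually lost

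*Combined protocol and SAP*

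**What the plan says.** All the relevant text is in section 12.0, Statistical Considerations.

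- The paragraph on the statistical analysis starts with an unadjusted comparison: "Mean BPs will be compared across groups using a two-sample, two-sided, 5% significance t-test".
- It then adds baseline BP without any condition: "The analysis will be then extended to gain statistical power by adjusting the comparison by baseline BP levels".
- It makes mixed-effects models the intention-to-treat analysis and closes with the rule at issue: "key variables (age, sex, race/ethnicity) will be compared across treatment groups and if different will be used in a multivariate mixed effects model".
- The opening Statistical Analysis Plan paragraph names the tools for checking balance ("We will apply the independent samples t-test and Chi-squared test to compare key measures between" the arms) but gives no significance level or size of imbalance.
- Other Statistical Considerations says "Sampling balance for the key predictors will be checked and adjusted for in the analysis" and lists no variables. On power it says "We address power for Aims 1 and 2 for unadjusted tests".

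Nowhere does the document fix age, sex and race/ethnicity as covariates in a BP model.

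**The concern.** A covariate earns its place by predicting the outcome. A test of balance between randomised arms carries no information on that: among all randomised patients, any difference in age, sex or race/ethnicity arose by chance. If analysed patients are compared instead, dropout also plays a part, and the plan does not say which group is meant.

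Two things are at stake. First, the adjusted mixed model cannot be known before the data are seen. With no threshold stated, two analysts could fit different models to the same data and both comply. Second, the trial usually forgoes precision from variables it already collects. The plan gives power as its reason for adjusting for baseline BP, and the same reason applies to variables it calls key.

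**Working it through.** **Inputs from section 12.0.** Standardised effect 0.25, SBP standard deviation 21 mmHg (so 5.25 mmHg), two-sided 5% t-test, 576 evaluable patients for 85% power, and 25% attrition.

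**The plan's own figure.** Per arm, n = 2(z₀.₉₇₅ + z_power)² / d².
- 85% power: 2(1.960 + 1.036)² / 0.0625 = 287.3, so 288 per arm and 576 in total, as stated.
- 80% power: 2(1.960 + 0.842)² / 0.0625 = 251.2, so 252 per arm and 504 in total, as stated.
- After attrition, 576 / 0.75 = 768 against the stated 770. The small difference does not matter here.

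**How often the rule adjusts for nothing.** Under randomisation a variable is flagged with probability equal to the test level a. For three independent tests (independence assumed), P(none flagged) = (1 − a)³.
- a = 0.05: 0.95³ = 0.857
- a = 0.10: 0.90³ = 0.729
- a = 0.20: 0.80³ = 0.512

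**What fixed adjustment is worth.** The documents give neither the correlation r between baseline and 6-month SBP nor the further share R² of 6-month SBP variance that the three variables explain, so both are assumed. With 288 per arm, power comes from the noncentral t with d = 0.25 / √(1 − r² − R²). The standard error is 21 × √[(1 − r² − R²) × 2/288].

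| r | R² | Power | Gain over baseline BP only (points) | SE, mmHg | SE reduction |
|---|---|---|---|---|---|
| 0.3 | 0 | 88.1% | – | 1.669 | – |
| 0.3 | 0.01 | 88.4% | 0.3 | 1.660 | 0.6% |
| 0.3 | 0.02 | 88.8% | 0.7 | 1.651 | 1.1% |
| 0.3 | 0.05 | 89.8% | 1.7 | 1.623 | 2.8% |
| 0.3 | 0.10 | 91.4% | 3.3 | 1.575 | 5.7% |
| 0.5 | 0 | 93.3% | – | 1.516 | – |
| 0.5 | 0.01 | 93.6% | 0.3 | 1.505 | 0.7% |
| 0.5 | 0.02 | 93.9% | 0.6 | 1.495 | 1.3% |
| 0.5 | 0.05 | 94.7% | 1.4 | 1.464 | 3.4% |
| 0.5 | 0.10 | 96.0% | 2.7 | 1.411 | 6.9% |

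**What the conditional rule keeps.** On the scale of the estimator's true variance, the share of the available reduction kept is 2[cφ(c) + 1 − Φ(c)], where c is the critical value of the balance test.
- a = 0.05, c = 1.960: 2(1.960 × 0.0584 + 0.025) = 0.28, so 72% is lost.
- a = 0.10: 0.44 kept, 56% lost.
- a = 0.20: 0.65 kept, 35% lost.

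The reported standard error does worse, because it shrinks only in trials where a variable enters. In simulation (576 patients, 10,000 trials per scenario, no baseline BP term, R² from 5% to 20%) the rule kept 2% to 4% of the reduction in reported standard error at a = 0.05. At a = 0.20 it kept 14% to 18%.

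**Power under the rule.** A simulation of 6,000 trials per scenario used a single-time-point ANCOVA in place of the mixed model. It had one continuous and two binary covariates, independent and of equal prognostic strength. Cells show baseline BP only / conditional rule / fixed adjustment, in per cent.

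| r, R² | a = 0.05 | a = 0.20 |
|---|---|---|
| 0.3, 0.05 | 87.4 / 87.7 / 88.9 | 87.9 / 88.5 / 89.5 |
| 0.3, 0.10 | 87.7 / 88.1 / 91.1 | 88.8 / 89.8 / 91.6 |
| 0.5, 0.05 | 93.8 / 94.0 / 95.2 | 93.7 / 94.1 / 94.8 |
| 0.5, 0.10 | 93.2 / 93.6 / 96.0 | 94.0 / 94.9 / 96.2 |

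The rule recovers 0.2 to 0.4 points at a = 0.05 and 0.4 to 1.0 at a = 0.20. Each is less than half of what fixed adjustment gains. In a repeat with other simulated trials, one scenario at a = 0.20 recovered about half.

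**Type I error.** At a = 0.05 the rule gave 5.1%, 4.3%, 4.8% and 4.4% in the four scenarios (Monte Carlo standard error 0.3 points). There is no inflation.

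**The case against.** The strongest reply is that little hangs on this. The rule governs the last extension in the list, after the t-test, the baseline-BP adjustment and the mixed models. Power was set for unadjusted tests, and the baseline-adjusted analysis already has 88% to 93% power under the assumptions above. No outcome data drive the selection, the three candidates are named in advance, and only eight subsets are possible. All of that is true. It limits the point to precision and pre-specification; it does not justify the rule.

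The size of the gain is also open. No R² is given, and a predominantly African-American and Latino sample may leave race/ethnicity little variance to explain. At 1% to 2% the gain is only 0.3 to 0.7 points, still at almost no cost. The claim that most of the precision is lost depends on the unstated threshold: on the true-variance scale it fails at 20%, while for reported standard error it holds there too.

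The sentence in Other Statistical Considerations has no conditional and could be read as a promise to adjust regardless. But it names no variables, so it does not override the explicit condition in the analysis paragraph. At best the two passages disagree, which is another reason to settle the wording.

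Finally, baseline BP is introduced as an extension of the t-test, and the mixed-model sentence does not repeat it. That is fair, and the replacement text should name baseline BP for both.

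**Conclusion.** The concern holds. The plan lets observed imbalance, with no threshold, decide whether age, sex and race/ethnicity enter the mixed-effects BP model. The failure to pre-specify needs no assumption. The loss of precision does:

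- With a 5% balance test and three independent variables, 85.7% of trials would adjust for none of them.
- With R² of 5% to 10% and r of 0.3 to 0.5, fixed adjustment is worth 1.4 to 3.3 power points and a standard error 2.8% to 6.9% smaller. The rule forgoes most of that.
- With R² near zero the loss is a fraction of a point.

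Type I error is not raised, and the unadjusted t-test stands as it is. This should be corrected, but it does not threaten the trial's validity.

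**What to change.** In the paragraph on the statistical analysis, replace the conditional clause with a statement such as: *Age, sex and race/ethnicity, together with baseline BP, are fixed covariates in the adjusted and mixed-effects BP models, whatever the observed balance.* State how each is coded, so that the model is fully determined before the data are seen.

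Align the two related sentences, in the opening Statistical Analysis Plan paragraph and in Other Statistical Considerations. Both should say that baseline comparisons are descriptive and do not select covariates. The unadjusted t-test may stay as a listed comparison.

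The cost is one rewritten sentence and two aligned ones, and a few degrees of freedom out of about 570. The sample size, rested on unadjusted tests, need not change, and no new data are required.

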## **13.0 REGULATORY REQUIREMENTS**

### **13.1 Informed Consent**

Written informed consent will be obtained from all subjects who present to the ED with eligibility criteria, namely elevated blood pressure consistent with stage I hypertension ( $\geq 140/90$ ). Patients will be shown a consent video to better streamline and standardize explanation of the study. Consent will be obtained from all subjects interested in participating after the entire study and its risks and hazards have been discussed and all of the subject's questions have been answered. Consent will only be obtained by study staff who have completed Human Subject Research Protection training. In order to minimize the possibility of coercion or undue influence on potential subjects, subjects will only be approached for study consent after they have completed their evaluation in the emergency department and have been identified for discharge. Subjects will also be informed that participation is voluntary and will not affect their relationship with the university/hospital if they decline to participate. Also, patients that are being cared for by the PI or key personnel will not be approached and consented by that individual but rather another member of the study team. Subjects will initially be identified by review of the tracking board listing in the department. The tracking board displays the patients' last name, room number, age, and vital signs. If patients meet the BP requirement (BP  $\geq 140/90$ ) and are slated for discharge from the emergency department, then the study personnel will approach the attending physician caring for the patient for preliminary review of

exclusion criteria. At no time during enrollment will any information be placed in the subjects' medical record.

All information collected in this study is confidential and all data will be transformed into anonymously-coded identifiers for each subject prior to analysis. We use a double coding system to maintain the confidentiality of information. Only [name] (PI) and study personnel will be able to link information to subjects. This is necessary because patients will be followed for a total of one year after discharge so participants will need to be tracked during this time. All data will be stored electronically on REDCap.

### **Data Characteristics:**

All data forms will be initially developed and tested on paper; Spanish language versions of participant questionnaires will be prepared and back-translated to English prior to obtaining certified translations; after thorough pilot testing, paper forms are to be converted to equivalent electronic data entry forms with use of REDCap. REDCap (Research Electronic Data Capture) is a secure, web-based application designed to support data capture for research studies, providing: 1) an intuitive interface for validated data entry; 2) audit trails for tracking data manipulation and export procedures; 3) automated export procedures for seamless data downloads to common statistical packages; and 4) procedures for importing data from external sources. At UI Health, REDCap is hosted on secure servers located in and supported by the Institute for Health Research and Policy (IHRP). Project staff will be trained in the use of REDCap for entry of study data. Appropriate logic and limits checking (including cross-form validity checks) will be implemented in REDCap to facilitate accurate and consistent data entry. Where practical, study data will be directly entered into the REDCap database by clinical staff. Alternatively, information can be captured on paper and entered into the system from the forms. Routinely throughout the study the REDCap database will be downloaded into a secure virtual computing environment (virtual servers and virtual workstations secured behind software and hardware firewalls) available through IHRP. Study information within the virtual environment will be available for participant tracking activities such as production of result and reminder letters, scheduling of interim telephone contacts, and scheduling and tracking of follow-up visits. Regular quality control and data cleaning/ error reports will be produced which identify missing,

out of range, and questionable values. These reports will be reviewed with study staff every two weeks. Errors will remain on reports until they are resolved. Statistical analyses prior to the 3 and 6-month outcome evaluations will be limited to quality control, enrollment and drop out reporting and participant demographics. No interim looks are anticipated but quality control and data entry errors and omissions will be continuously monitored and reported to staff for remediation.

### **13.2 Subject Confidentiality**

The PI is responsible for protecting the confidentiality of subjects' data. All data will be entered into electronic database (REDcap). There will be no paper charts/data entry. This will minimize the potential for loss of information and breech of privacy. All of this information will be handled in accordance with HIPAA guidelines.

Patient confidentiality will be maintained through secured, password protection computerized data collection. All documents and information about this study will be kept confidential in accordance with federal, state, and local laws and regulations. Medical records and data generated by the study may be reviewed by the **UIC Institutional Review Board**, and **The Office For Human Research Protections**, to assure proper conduct of the study and compliance with federal regulations. The results of this study will be published. If results are published, no subject will be identified by name.

### **13.3 Unanticipated Problems**

Any unanticipated problems will be addressed immediately by the PI and brought to the DSMB. Any unanticipated problems will also be reported and documented in written document to the IRB and sponsor (if applicable).

